12. APPENDIX A

SF-36 QUESTIONNAIRE

Name: _____

Ref. Dr: _____

Date: _____

ID#: _____

Age: _____

Gender: M / F

Please answer the 36 questions of the **Health Survey** completely, honestly, and without interruptions.

GENERAL HEALTH:

In general, would you say your health is:

Excellent Very Good Good Fair Poor

Compared to one year ago, how would you rate your health in general now?

Much better now than one year ago
 Somewhat better now than one year ago
 About the same
 Somewhat worse now than one year ago
 Much worse than one year ago

LIMITATIONS OF ACTIVITIES:

The following items are about activities you might do during a typical day. Does your health now limit you in these activities? If so, how much?

Vigorous activities, such as running, lifting heavy objects, participating in strenuous sports.

Yes, Limited a lot Yes, Limited a Little No, Not Limited at all

Moderate activities, such as moving a table, pushing a vacuum cleaner, bowling, or playing golf

Yes, Limited a Lot Yes, Limited a Little No, Not Limited at all

Lifting or carrying groceries

Yes, Limited a Lot Yes, Limited a Little No, Not Limited at all

Climbing several flights of stairs

Yes, Limited a Lot Yes, Limited a Little No, Not Limited at all

Climbing one flight of stairs

Yes, Limited a Lot Yes, Limited a Little No, Not Limited at all

Bending, kneeling, or stooping

Yes, Limited a Lot Yes, Limited a Little No, Not Limited at all

Walking more than a mile

Yes, Limited a Lot Yes, Limited a Little No, Not Limited at all

Walking several blocks

Yes, Limited a Lot Yes, Limited a Little No, Not Limited at all

Walking one block

Yes, Limited a Lot Yes, Limited a Little No, Not Limited at all

TENS for Neuropathic Pain in NMOSD

Principal Investigator: [name], PhD

Bathing or dressing yourself

Yes, Limited a Lot

Yes, Limited a Little

No, Not Limited at all

PHYSICAL HEALTH PROBLEMS:

During the past 4 weeks, have you had any of the following problems with your work or other regular daily activities as a result of your physical health?

Cut down the amount of time you spent on work or other activities

Yes

No

Accomplished less than you would like

Yes

No

Were limited in the kind of work or other activities

Yes

No

Had difficulty performing the work or other activities (for example, it took extra effort)

Yes

No

EMOTIONAL HEALTH PROBLEMS:

During the past 4 weeks, have you had any of the following problems with your work or other regular daily activities as a result of any emotional problems (such as feeling depressed or anxious)?

Cut down the amount of time you spent on work or other activities

Yes

No

Accomplished less than you would like

Yes

No

Didn't do work or other activities as carefully as usual

Yes

No

SOCIAL ACTIVITIES:

Emotional problems interfered with your normal social activities with family, friends, neighbors, or groups?

Not at all

Slightly

Moderately

Severe

Very Severe

PAIN:

How much bodily pain have you had during the past 4 weeks?

None

Very Mild

Mild

Moderate

Severe

Very Severe

During the past 4 weeks, how much did pain interfere with your normal work (including both work outside the home and housework)?

Not at all

A little bit

Moderately

Quite a bit

Extremely

TENS for Neuropathic Pain in NMOSD

Principal Investigator: [name], PhD

ENERGY AND EMOTIONS:

These questions are about how you feel and how things have been with you during the last 4 weeks. For each question, please give the answer that comes closest to the way you have been feeling.

Did you feel full of pep?

- All of the time
- Most of the time
- A good Bit of the Time
- Some of the time
- A little bit of the time
- None of the Time

Have you been a very nervous person?

- All of the time
- Most of the time
- A good Bit of the Time
- Some of the time
- A little bit of the time
- None of the Time

Have you felt so down in the dumps that nothing could cheer you up?

- All of the time
- Most of the time
- A good Bit of the Time
- Some of the time
- A little bit of the time
- None of the Time

Have you felt calm and peaceful?

- All of the time
- Most of the time
- A good Bit of the Time
- Some of the time
- A little bit of the time
- None of the Time

Did you have a lot of energy?

- All of the time
- Most of the time
- A good Bit of the Time
- Some of the time
- A little bit of the time
- None of the Time

TENS for Neuropathic Pain in NMOSD

Principal Investigator: [name], PhD

Have you felt downhearted and blue?

- All of the time
- Most of the time
- A good Bit of the Time
- Some of the time
- A little bit of the time
- None of the Time

Did you feel worn out?

- All of the time
- Most of the time
- A good Bit of the Time
- Some of the time
- A little bit of the time
- None of the Time

Have you been a happy person?

- All of the time
- Most of the time
- A good Bit of the Time
- Some of the time
- A little bit of the time
- None of the Time

Did you feel tired?

- All of the time
- Most of the time
- A good Bit of the Time
- Some of the time
- A little bit of the time
- None of the Time

SOCIAL ACTIVITIES:

During the past 4 weeks, how much of the time has your physical health or emotional problems interfered with your social activities (like visiting with friends, relatives, etc.)?

- All of the time
- Most of the time
- Some of the time
- A little bit of the time
- None of the Time

TENS for Neuropathic Pain in NMOSD

Principal Investigator: [name], PhD

GENERAL HEALTH:

How true or false is each of the following statements for you?

I seem to get sick a little easier than other people

Definitely true

Mostly true

Don't know

Mostly false

Definitely false

I am as healthy as anybody I know

Definitely true

Mostly true

Don't know

Mostly false

Definitely false

I expect my health to get worse

Definitely true

Mostly true

Don't know

Mostly false

Definitely false

My health is excellent

Definitely true

Mostly true

Don't know

Mostly false

Definitely false

TENS for Neuropathic Pain in NMOSD

Principal Investigator: [name], PhD

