2.3. Secondary

Six secondary objectives are intended to collect additional information about the potential benefit of QUELL FLEX:

- A. The difference in pain scores at the end of the open label phase compared to the end of the initial blinded phase.
- B. A change in the “worst” pain score in the treatment arm vs. the sham arm between the baseline screening call and week 4; and the change in the “worst” pain from baseline to week 8 for all subjects.
- C. A change in the “average” pain score in the treatment arm vs. the sham arm between the baseline screening call and week 4; and the change in the “average” pain from baseline to week 8 for all subjects.
- D. The number of patients who withdraw because of poor compliance. We expect a higher withdrawal and non-compliance rate in the sham group.
- E. Quality of life surveys will be conducted before and after the treatment phase and at the end of the study to determine if the QUELL FLEX treatment impacts overall quality of life.
- F. Reduction in pain medication use over the course of the study.

TENS for Neuropathic Pain in NMOSD

Principal Investigator: [name], PhD

3. Hypotheses

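### One of the two social-activities items on the Appendix A SF-36 form has no recall period, names only emotional causes and has response options that do not grade interference

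*Combined protocol and SAP*

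**What the plan says.** Section 2.3, objective E, gives the purpose of the quality-of-life measurement as "to determine if the QUELL FLEX treatment impacts overall quality of life". On timing, the same objective states: "Quality of life surveys will be conducted before and after the treatment phase and at the end of the study". Sections 6.5.1.1 (steps 1, 10 and 11), 6.5.1.2 and 9.2 place the SF-36 at the start, at the end of the 4-week blinded phase and at the end of the 4-week open-label phase. It is the only quality-of-life instrument described in section 6.6.2, and section 9.2 has it conducted by Zoom.

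Appendix A prints the form. Under the first Social Activities heading the whole question is "Emotional problems interfered with your normal social activities with family, friends, neighbors, or groups", with the options *Not at all*, *Slightly*, *Moderately*, *Severe*, *Very Severe*. Under the second Social Activities heading the question begins "During the past 4 weeks, how much of the time has your physical health or emotional problems interfered with your social activities", with options that grade frequency.

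Section 11.3 relates the change in pain score to the change in each quality-of-life variable. It states no SF-36 version, subscale or scoring rule.

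**The concern.** The two social items differ in time window, in the causes they admit and in response scale, and the first is not a complete question. Three consequences follow.

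- **Time.** The first item uses the past tense without a window. A week-4 answer may take in time before treatment, and a week-8 answer may take in the blinded phase.
- **Cause.** Under section 5.1.6 the patients' pain is localized to a spinal cord lesion, and section 3.2 expects quality of life to improve because pain drives it. The first item does not ask about direct physical or pain-related interference with social life.
- **Scale.** The upper two options are words for severity, not for degree of interference. Because staff ask the questions over Zoom, an ungrammatical question with mismatched answers invites rephrasing that could differ from one visit to the next.

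At stake is the clarity of one component of a secondary objective.

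**Working it through.** No power or sample-size calculation bears on this point. The check is an item count and a comparison of wordings.

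**1. Is the form complete?** It introduces itself with "Please answer the 36 questions of the" survey. Counting the printed items by block: general health 2, activities 10, physical problems 4, emotional problems 3, first social item 1, pain 2, energy and emotions 9, second social item 1, closing general-health statements 4.

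2 + 10 + 4 + 3 + 1 + 2 + 9 + 1 + 4 = 36. The stated number is reproduced, so no item is missing.

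**2. What time frame does each item carry?**

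| Time frame | Items | Count |
|---|---|---|
| Past 4 weeks | physical problems 4, emotional problems 3, pain 2, energy and emotions 9, second social item 1 | 19 |
| Now ("Does your health now limit you in these activities") | activities | 10 |
| Present state | overall health 1, closing statements 4 | 5 |
| Compared with one year ago | health transition | 1 |
| None | first social item | 1 |

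19 + 10 + 5 + 1 + 1 = 36. The first social item is the only one without a time frame. It is 1/36 = 2.8% of the items and 1/2 = 50% of the social-activities items.

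**3. Could a window carry over from the block above?** The emotional-problems block opens with "During the past 4 weeks, have you had any of the following problems with your work or other regular daily activities as a result of" emotional problems. That stem concerns work and daily activities and takes Yes/No answers. A new heading then separates it from the social item, which has a different subject and a five-point scale. As printed, the 4-week window does not carry over.

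**4. The item beside its closest comparators on the same form.**

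| | First social item | Second social item | Pain-interference item |
|---|---|---|---|
| Stem | "Emotional problems interfered with your normal social activities with family, friends, neighbors, or groups" | "During the past 4 weeks, how much of the time has your physical health or emotional problems interfered with your social activities" | "During the past 4 weeks, how much did pain interfere with your normal work" |
| Window | none | 4 weeks | 4 weeks |
| Causes | emotional only | physical or emotional | pain |
| Options | *Not at all* to *Very Severe* | *All of the time* to *None of the Time* | *Not at all* to *Extremely* |

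The pain-interference item shows how the form grades interference elsewhere: every option is a word of degree. In the first social item the scale changes from degree to severity after *Moderately*. *Severe* and *Very Severe* are also the last two options of the bodily-pain item that follows it.

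**5. What reaches the analysis?** The form is given three times, so every item, this one included, yields a baseline, a week-4 and a week-8 answer. Each phase lasts 4 weeks (section 2.1), the same length as the second social item's window. That item is therefore tied to each phase; the first is not. As section 11.3 gives no scoring rule, nothing in the plan says whether or how the two are combined.

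**The case against.** The strongest reply is that little depends on this item. Sixteen other items also lack a 4-week recall, and a repeated present-state answer still gives a change score. Physical limits are asked about in the 10 activity items and the 4 physical-problem items, pain interference has its own item, and the second social item covers physical causes. A question on emotional causes alone is not inconsistent in itself, since the form already separates physical from emotional blocks, and section 11.3 names anxiety and depressive symptoms in its hypothesis. Both arms answer the same form, so nothing suggests that the wording favours either one.

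Most of this stands, and it limits the point. The answer on recall is that each of those 16 items has a frame of its own (now, present state or one year ago), while this item has none. The answer on cause is that the problem lies in pairing this item with a companion that asks about something wider. The mismatch in the options is not met by any of these arguments.

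It may also be said that words were lost from the stem when the form was reproduced. That cannot be excluded. But the line begins with a capital letter and reads as a whole printed line, and lost stem words would not explain the response options.

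A reader might infer that part of objective E goes unmeasured over the trial phases. The documents do not support that: the whole form is given at all three times, and the companion item covers both causes over a window equal to the phase length.

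**Conclusion.** The defect is real, internal to the form and minor. One item of 36, and one of the two on social activities, is a fragment with no time frame, restricted to emotional causes and answered on a scale that changes meaning partway. A social score built from both items would mix different windows, causes and scales. The primary endpoint rests on the Numerical Pain Scale, so it and the sample size are untouched.

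A reader might go on to infer that the item would roughly halve the measured change in social functioning. That needs a two-item score with equal weights and almost no change on this item: if the companion changes by d and this item by 0, the mean change is (d + 0)/2 = d/2. The plan defines no such score and gives no data on how this item would change, so the halving is not a finding.

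Nor do the documents show that the item departs from the published instrument, because they do not reproduce the source wording. The conclusion rests on the form's own inconsistency and assumes that patients are asked the item as Appendix A prints it.

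**What to change.** Before further use, check this item against the source SF-36 form and replace its stem and options with the instrument's own wording. Use the same form at all visits and in both arms.

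If forms have already been completed, report which wording was used at each visit and flag the item in the quality-of-life analysis.

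The cost is a form update. Answers to this item before and after the correction will not be directly comparable, so a patient whose visits straddle the change has no clean change score on it.
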